9.11. Type and Duration of Follow-up of Subjects after Adverse Events

AEs will be followed until resolution or stability even if this extends beyond the study-reporting period. Resolution of an AE is defined as the return to pretreatment status or stabilization of the condition with the expectation that it will remain chronic.

Follow-up procedures, evaluations, and outcomes will be recorded on the subject's CRFs.

9.12. Halting Rules

9.12.1. Halting Criteria for the Study

Study dosing may be halted after review of data by the MM in consultation with RGS ML. The Data Safety Monitoring Board (DSMB) will be informed and a review of available safety data will be conducted by the DSMB if any of the following occur:

- Death of a subject following injection and prior to the subject's last visit that was possibly related to study product
- Two Grade 4 non-laboratory AE (as per FDA guidance toxicity table as modified in [Appendix B](#)) related to study treatment, or

- One life-threatening allergic/hypersensitivity reaction (anaphylaxis) in any subject, manifested by bronchospasm with or without urticaria or angioedema, or
- Requiring hemodynamic support with pressor medications or mechanical ventilation, or
- One SAE that is considered definitely or possibly related to study product
- Four or more subjects with a Grade 3 AE in the same organ class (systemic toxicity, clinical laboratory tests or vital signs) possibly related to study drug

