9.8.2. Serious Adverse Events

An SAE is any untoward medical occurrence that at any dose:

- Results in death
- Is life-threatening*
- Requires inpatient hospitalization or prolongation of existing hospitalization
- Congenital anomaly/birth defect

- Persistent or significant incapacity or substantial disruption of the ability to conduct normal life functions

**Life-threatening AE. An AE is considered “life-threatening” if, in the view of either the Investigator or Sponsor, its occurrence places the patient or subject at immediate risk of death. It does not include an AE that, had it occurred in a more severe form, might have caused death.*

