9.9. Methods and Timing for Assessing, Recording, and Analyzing Safety Parameters

9.9.1. Adverse Events

AEs will be collected at Day 1 during and after dosing. Any medical condition that is present at the time that the subject is screened should be considered as baseline and not reported as an AE. However, if the condition increases in severity or frequency at any time during the study, it should be recorded as an AE.

All AEs must be graded for severity and relationship to study product based on the Investigator’s assessment.

The Investigator will assess the intensity of AEs based on the following definitions per Toxicity Table (modified from FDA Toxicity Grading Scale for Healthy Adult and Adolescent Volunteers Enrolled in Preventive Vaccine Clinical Trials):

- Mild: Grade 1 (awareness of sign or symptom, but easily tolerated)
- Moderate: Grade 2 (discomfort sufficient to cause interference with normal activities)
- Severe: Grade 3 (incapacitating, with inability to perform normal activities)
- Potentially Life Threatening: (Grade 4)

- Death: (Grade 5)

It is important to distinguish between serious and severe AEs. Severity is a measure of intensity whereas seriousness is defined by the criteria in [Section 9.8.2](#).

An AE of severe intensity need not necessarily be considered serious. For example, nausea that persists for several hours may be considered severe nausea, but not an SAE. On the other hand, a stroke that results in only a limited degree of disability may be considered a mild stroke but would be an SAE.

For an AE to be a suspected drug-related event, there should be at least a reasonable possibility of a causal relationship between the study drug and the AE.

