*Will not be used as halting criteria

	Mild (Grade 1)	Moderate (Grade 2)	Severe (Grade 3)	Potentially Life Threatening (Grade 4)**
Sodium – Hyponatremia mEq/L	132 – 134	130 – 131	125 – 129	< 125
Sodium – Hypernatremia mEq/L	144 – 145	146 – 147	148 – 150	> 150
Potassium – Hyperkalemia mEq/L	5.1 – 5.2	5.3 – 5.4	5.5 – 5.6	> 5.6
Potassium – Hypokalemia mEq/L	3.5 – 3.6	3.3 – 3.4	3.1 – 3.2	< 3.1
Glucose – Hypoglycemia mg/dL	65 – 69	55 – 64	45 – 54	< 45
Glucose – Hyperglycemia Fasting – mg/dL Random – mg/dL	100 – 110 110 – 125	111 – 125 126 – 200	>125 >200	Insulin requirements or hyperosmolar coma
BUN mg/dL	23 – 26	27 – 31	> 31	Requires dialysis
Creatinine – mg/dL	1.5 – 1.7	1.8 – 2.0	2.1 – 2.5	> 2.5 or requires dialysis

Calcium – hypocalcemia mg/dL	8.0 – 8.4	7.5 – 7.9	7.0 – 7.4	< 7.0
Calcium – hypercalcemia mg/dL	10.5 – 11.0	11.1 – 11.5	11.6 – 12.0	> 12.0
Magnesium – hypomagnesemia mg/dL	1.3 – 1.5	1.1 – 1.2	0.9 – 1.0	< 0.9
Phosphorous – hypophosphatemia mg/dL	2.3 – 2.5	2.0 – 2.2	1.6 – 1.9	< 1.6
CPK – mg/dL	1.25 – 1.5 x ULN***	1.6 – 3.0 x ULN	3.1 – 10 x ULN	> 10 x ULN
Albumin – Hypoalbuminemia g/dL	2.8 – 3.1	2.5 – 2.7	< 2.5	--
Total Protein – Hypoproteinemia g/dL	5.5 – 6.0	5.0 – 5.4	< 5.0	--
Alkaline phosphate – increase by factor	1.1 – 2.0 x ULN	2.1 – 3.0 x ULN	□ 3.1 – 10 x ULN	> 10 x ULN
LFTs –ALT, AST increase by factor	1.1 – 2.5 x ULN	2.6 – 5.0 x ULN	5.1 – 10 x ULN	> 10 x ULN
Bilirubin – when accompanied by any increase in LFT increase by factor	1.1 – 1.25 x ULN	1.26 – 1.5 x ULN	1.51 – 1.75 x ULN	> 1.75 x ULN
Bilirubin – when LFT is normal; increase by factor	1.1 – 1.5 x ULN	1.6 – 2.0 x ULN	2.0 – 3.0 x ULN	> 3.0 x ULN
Cholesterol	201 – 210	211 – 225	> 226	---
Pancreatic enzymes – amylase, lipase	1.1 – 1.5 x ULN	1.6 – 2.0 x ULN	2.1 – 5.0 x ULN	> 5.0 x ULN

[figure not shown]
Hematology	Mild (Grade 1)	Moderate (Grade 2)	Severe (Grade 3)	Potentially Life Threatening (Grade 4)
Hemoglobin (Female) - gm/dL	11.0 – 12.0	9.5 – 10.9	8.0 – 9.4	< 8.0
Hemoglobin (Female) change from baseline value - gm/dL	Any decrease – 1.5	1.6 – 2.0	2.1 – 5.0	> 5.0
Hemoglobin (Male) - gm/dL	12.5 – 13.5	10.5 – 12.4	8.5 – 10.4	< 8.5
Hemoglobin (Male) change from baseline value – gm/dL	Any decrease – 1.5	1.6 – 2.0	2.1 – 5.0	> 5.0
WBC Increase - cell/mm ³	10,800 – 15,000	15,001 – 20,000	20,001 – 25,000	> 25,000
WBC Decrease - cell/mm ³	2,500 – 3,500	1,500 – 2,499	1,000 – 1,499	< 1,000
Lymphocytes Decrease - cell/mm ³	750 – 1,000	500 – 749	250 – 499	< 250

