Absolute Neutrophils Decrease - cell/mm ³	1,500 – 2,000	1,000 – 1,499	500 – 999	< 500
Eosinophils - cell/mm ³	650 – 1500	1501 - 5000	> 5000	Hypereosinophilic
Platelets Decreased - cell/mm ³	125,000 – 140,000	100,000 – 124,000	25,000 – 99,000	< 25,000
PT – increase by factor	1.0 – 1.10 x ULN	□ 1.11 – 1.20 x ULN	1.21 – 1.25 x ULN	> 1.25 ULN
PTT – increase by factor	1.0 – 1.2 x ULN	1.21 – 1.4 x ULN	1.41 – 1.5 x ULN	> 1.5 x ULN
Fibrinogen increase - mg/dL	400 – 500	501 – 600	> 600	--
Fibrinogen decrease - mg/dL	150 – 200	125 – 149	100 – 124	< 100 or associated with gross bleeding or DIC

Abbreviations: CPK = creatine phosphokinase; DIC = disseminated intravascular coagulation; LFT = liver function test; ULN = upper limit of normal.

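### As worded, Protocol 9.12.1 forces a DSMB review for four Grade 3 laboratory AEs but for no number of non-serious Grade 4 laboratory AEs

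*Protocol*

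**What the plan says.** Section 9.12.1 of Protocol v4.0 lets the Medical Monitor, in consultation with the sponsor's Medical Lead, halt dosing. It also states that the DSMB will be informed and will review the data if any listed criterion is met. Three of the criteria bear on laboratory AEs:

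- **Grade 4:** "Two Grade 4 non-laboratory AE (as per FDA guidance toxicity table as modified in" Appendix B), related to study treatment. Laboratory AEs are outside it.
- **Serious events:** one SAE judged definitely or possibly related.
- **Grade 3 cluster:** "Four or more subjects with a Grade 3 AE in the same organ class (systemic toxicity, clinical laboratory tests or vital signs"). The AEs must also be judged possibly related. This is the only criterion that mentions laboratory tests.

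The remaining criteria (death, anaphylaxis, pressor or ventilator support) do not describe a non-serious laboratory abnormality.

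Grade and seriousness are kept apart. Section 9.9.1 says "Severity is a measure of intensity whereas seriousness is defined by the criteria in" Section 9.8.2. The five criteria there are clinical, for instance "Requires inpatient hospitalization or prolongation of existing hospitalization". An event is life-threatening only if, in the view of the Investigator or Sponsor, "its occurrence places the patient or subject at immediate risk of death". Appendix B labels Grade 4 only as potentially life-threatening and assigns it to most laboratory tests by a numeric cut-off.

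**The concern.** A safety trigger should not become harder to meet as the events become more severe. Here two wordings combine to produce that result: the non-laboratory limit in the Grade 4 criterion, and the absence of any *or higher* in the Grade 3 criterion. Neither would cause it alone. A cluster of related laboratory abnormalities that forces a review at Grade 3 drops out of the mandatory rule at Grade 4, unless an event also meets a seriousness criterion.

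What is at stake is the obligation to convene the DSMB between planned meetings. Without it, the more severe cluster is left to the judgement of the Medical Monitor and Medical Lead.

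**Working it through.** The plan states no figure to reproduce. The check applies the rule as written to hypothetical sets of AEs.

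**Inputs**

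- Section 9.12.1: the three criteria above.
- Section 9.9.2: relationship has three separate categories, definitely, possibly and not related.
- Appendix B, row "Potassium – Hyperkalemia mEq/L": Grade 3 is 5.5–5.6 and Grade 4 is above 5.6.
- Appendix B, row "PT – increase by factor": Grade 3 is 1.21–1.25 × ULN and Grade 4 is above 1.25 × ULN.
- Appendix A, Table 3: potassium and PT are both in the Cohort 4 chemistry panel.
- Section 5.1: Cohort 4 safety labs after dosing are on Days 15, 45 and 120 only, so an AE can be first found above the narrow Grade 3 band.

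**Rule.** Let N be the number of subjects with a laboratory AE that the last criterion counts. A review is forced if N ≥ 4.

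- As written: grade = 3 and possibly related.
- First edit only: grade ≥ 3 and possibly related.
- Both edits: grade ≥ 3 and definitely or possibly related.

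**Results for non-serious laboratory AEs in one class**

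| Subjects with AEs | N as written | N, first edit | N, both edits |
|---|---|---|---|
| 4 Grade 3, possibly related | 4, review | 4, review | 4, review |
| 3 Grade 3 + 1 Grade 4, possibly related | 3, none | 4, review | 4, review |
| 1 Grade 4, possibly related | 0, none | 1, none | 1, none |
| 4 Grade 4, possibly related | 0, none | 4, review | 4, review |
| 10 Grade 4, possibly related | 0, none | 10, review | 10, review |
| 4 Grade 3, definitely related | 0, none | 0, none | 4, review |
| 4 Grade 4, definitely related | 0, none | 0, none | 4, review |

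A single related Grade 4 laboratory AE that is also serious forces a review in every column, through the SAE criterion.

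**In laboratory units.** Four subjects with possibly related, non-serious hyperkalemia AEs at 5.6 mEq/L meet the criterion; four first found at 5.7 mEq/L do not. The same holds for PT at 1.25 versus 1.26 × ULN.

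The contrast is cleanest for AEs first found at Grade 4. Section 9.10.1 records maximum intensity for each AE, but Section 9.12.1 does not say which grade of a worsening AE is counted.

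**The case against.** **Grade 3 may be meant as a floor.** A sensible Medical Monitor might read it that way, and then the problem disappears. The text does not say so, however. SAP 9.10.1 writes Grade 3 or greater where both grades are meant, so the study documents have an explicit form for this. A rule that obliges a review should not depend on the reader.

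**The omission may be deliberate.** Isolated Grade 4 laboratory values are often transient or spurious, and keeping them out of the two-event criterion is defensible. That does not explain counting four Grade 3 laboratory AEs while ignoring four at Grade 4, and the documents give no reason for it.

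**Appendix B notes cannot be fully read.** The note "Will not be used as halting criteria" has no visible anchor in the supplied text, and a double asterisk on the laboratory Grade 4 column has no visible text. Either could change how laboratory grades enter halting. The first cannot exclude all laboratory results, because the criterion itself names laboratory tests. This uncertainty stands until the original is checked.

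**Other safeguards exist.** This also stands, and it sets the size of the point. The Medical Monitor may halt dosing (9.12.1), and either the Medical Monitor or the Medical Lead may recommend convening the DSMB (9.13.1, 9.13.2). The DSMB reviews data periodically (9.13.3) and receives laboratory summaries and listings, with one meeting planned for Cohort 4 (SAP 4.2).

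A reader might infer that severe laboratory toxicity could escape the DSMB altogether. The documents do not support that: these routes remain open, and one related serious event is enough to force a review. Nor does a Grade 4 label by itself make an event serious and so close the gap, since Section 9.8.2 requires immediate risk of death or another listed clinical outcome.

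**Conclusion.** The point holds as a minor defect of wording in v4.0. For possibly related, non-serious laboratory AEs, the mandatory trigger is met by four subjects at Grade 3 and by no number at Grade 4. The same criterion, read equally strictly, also omits definitely related events.

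What is lost is only the obligation to hold an ad hoc review. Section 3.1.3 states that Cohorts 1-3 have finished their visits. Cohort 4 receives a single dose, so a halt could protect only Cohort 4 subjects not yet dosed when earlier subjects' laboratory results arrive. The documents do not say how many that is.

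It would be tempting to attach a probability of a missed review. The documents give no rate of related Grade 3 or 4 laboratory AEs, no share first found at Grade 4 and no enrolment pace, so any such figure would be pure assumption.

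The conclusion assumes that the criteria are applied as written and that the Appendix B notes do not alter them. It applies to v4.0 only: the SAP cites protocol v5.0 of 06-JAN-2025, which was not supplied.

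**What to change.** In the last criterion of Section 9.12.1, replace Grade 3 with *Grade 3 or higher*, and possibly related with *definitely or possibly related*. Keep the count of four and the three classes, and align the DSMB charter. Both edits are needed: the table shows that the first alone still misses definitely related events.

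The non-laboratory limit in the Grade 4 criterion can stay, so an isolated non-serious Grade 4 laboratory AE would still force no review. The edits apply to systemic toxicity and vital signs as well, because the criterion covers all three classes.

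Before amending, check whether v5.0 already has this wording, in which case nothing is needed, and read the Appendix B halting note and the double-asterisk note in the original.

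The cost is one line in an amendment with IRB approval (Protocol 13.2), a charter check, and an occasional extra ad hoc review.

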9.13. Safety Oversight

9.13.1. ICON Medical Monitor

The ICON MM is the clinical site's primary point of contact for eligibility or safety related questions. The ICON MM is responsible for liaising with RGS ML to ensure that all medical concerns are communicated and will provide any potential pertinent medical communication update to the project team as needed. As well as make a recommendation that the DSMB be convened to review any safety concerns.

The ICON MM will communicate with the RGS ML for any safety related questions. The ICON MM will participate in the planned DSMB meetings and make recommendations that the DSMB be convened to review any safety concerns.

9.13.2. Resilience Government Services (RGS) Medical Lead

The RGS ML will be the main point of contact for the ICON MM including any safety-related questions or concerns. The RGS ML will escalate any medical or safety concerns to the DOD as needed. The RGS ML will participate in the planned DSMB meetings and can make a recommendation that the DSMB be convened to review any safety concerns.

9.13.3. Data Safety Monitoring Board (DSMB)

A centralized, independent DSMB will be established in collaboration with RGS and ICON. The DSMB will review blinded safety data and make safety and tolerability recommendations. More details on the role of and the data provided to the DSMB will be described in a DSMB Charter. See [Section 11.2](#) for more details on planned interim analyses.

The DSMB will periodically review accumulating blinded safety data by group. Prior to each meeting, the ICON statistician will provide the DSMB with AE data. Reports will be cumulative, generated from an up-to-date data file. Based on the reports, the DSMB will determine whether to recommend that the study should be continued, modified, or stopped for safety reasons.

The DSMB may recommend any steps to ensure the safety of study participants and the integrity of the trial. Furthermore, the DSMB may recommend that the trial be terminated or that specific groups be withdrawn from the study, if any subgroup manifests serious or widespread side effects. To guarantee the unrestricted performance of its task, the DSMB may receive the individual study morbidity and mortality data from the ICON unblinded statistician.

10. CLINICAL MONITORING

10.1. Direct Access to Source Data/Documents

The site will maintain appropriate medical and research records for this trial, in compliance with ICH E6(R2) GCP, Section 4.9, and regulatory and institutional requirements for the protection of confidentiality of subjects. As part of participating in a DOD-affiliated, or manufacturer-sponsored study, the site will permit authorized representatives of the sponsor(s), DOD, and regulatory agencies to review (and, when required by applicable law, to copy) clinical records for the purposes of quality assurance reviews, audits, and evaluation of the study safety and progress.

Forms for use as source document will be derived from the eCRFs provided to site by ICON. Additional source data are all information, original records of clinical findings, observations, or other activities in a clinical trial necessary for the reconstruction and evaluation of the trial. Examples of these original documents and data records include, but are not limited to, hospital records, clinical and office charts, laboratory notes, memoranda, pharmacy dispensing records, recorded data from automated instruments, copies or transcriptions certified after verification as being accurate and complete, microfiches, photographic negatives, microfilm or magnetic media, x-rays, and subject files and records kept at the pharmacy, laboratories, and medico-technical departments involved in the clinical trial. If data is recorded directly into the eCRF with no paper source, then that data should be listed as being a direct electronic data entry with no paper source available.

10.2. Study Monitoring

The Investigator shall permit the Site Monitor to review study data as frequently as deemed necessary to ensure that data are being recorded in an adequate manner and that protocol adherence is satisfactory.

The Investigator shall provide access to medical records for the Monitor in order that entries in the CRF may be verified. The Investigator, as part of his/her responsibilities, is expected to cooperate with ICON in ensuring that the study adheres to GCP requirements.

The Investigator may not recruit subjects into the study until such time that a visit, or with the agreement of the Sponsor, attendance at the Site Initiation Visit (SIV), has been made by a sponsor/ICON monitor to conduct a detailed review of the protocol and CRF.

Clinical monitors will verify that the clinical trial is conducted, and data are generated, documented (recorded), and reported in compliance with the protocol, GCP, and the applicable regulatory requirements. Clinical monitoring reports will be submitted to RGS.

10.3. Site Monitoring Plan

Site monitoring is conducted to ensure that the human subject protection, study and laboratory procedures, study intervention administration, and data collection processes are of high quality and meet Sponsor, GCP/ICH and, when appropriate, regulatory guidelines. Site visits may be conducted by an authorized representative of ICON, the IRB, and other regulatory or government agencies to inspect study data, subjects' medical records, and eCRFs in accordance

with ICH guidelines, GCP and the respective local and national government and local regulations and guidelines.

The Investigator will permit authorized representatives of ICON and the respective local and national health authorities to inspect facilities and records relevant to this study, if needed.

A separate monitoring plan, to be developed by ICON, will describe protocol-specific items to be monitored.

11. STATISTICAL CONSIDERATIONS

11.1. Sample Size Considerations

No formal sample size calculations were performed for this Phase 2 study, as there is no planned formal hypothesis testing, and the target enrollment of subjects was based on previous experiences from studies conducted with similar products.

11.2. Planned Interim Analysis

An interim Clinical Study Report (CSR) is planned for the first 125 subjects across the first three cohorts through Day 120. The data cut will be taken when all 125 subjects have completed their Day 120 visit for PD, PK, and ADA analysis. All available safety from subjects in Cohorts 1-3 will be included until the data cutoff for the DSMB report. The objectives of this interim CSR will be to compare safety between the 3 cohorts and to evaluate lot-to-lot variation in PK, PD and immunogenicity parameters within drug dose levels as defined in the SAP.

11.3. Statistical Analysis Plan

A formal Statistical Analysis Plan (SAP) will be developed with mock tables, listings, and figures (TLFs). The ICH Guidance Document E9 (Statistical Principles for Clinical Trials) will be followed for all statistical content. For categorical data, summaries of frequencies and percentages will be presented. Summaries for continuous data will include minimum, lower quartile, median, mean, standard deviation, upper quartile, and maximum. PD, PK and ADA continuous data will include additional summary statistics as described below and in the SAP.

11.4. Analysis Populations

Analysis populations for statistical analyses include intent-to-treat (ITT), safety, per-protocol (PP) and PD and PK populations as shown in [Table 1](#).

Table 1: Analysis Populations

Population	Description
Intention-to-Treat (ITT)	All subjects who were randomized. They will be analyzed according to the treatment group to which they were randomized.
Safety	All randomized subjects who received any study drug. They will be analyzed according to the treatment they actually received.
Per-Protocol (PP)	All subjects in the ITT population who have received all planned study drug, have no major excluding protocol deviations and will be analyzed according to the group to which they are randomized.
Pharmacodynamic (PD)	All Safety population subjects who have sufficient evaluable PD result following dosing. They will be analyzed according to the treatment they actually received.
Pharmacokinetic (PK)	All Safety Population subjects who have sufficient evaluable PK result following dosing.

	They will be analyzed according to the treatment they actually received.
--	--

11.5. Statistical Methods

For continuous variables, descriptive statistics will include the number of available records for evaluation, mean, standard deviation, Q1, median, Q3, minimum and maximum. For categorical variables, frequencies and percentages will be calculated for each category. Geometric means, coefficients of variation (%), geometric coefficients of variation (%) and the geometric coefficient of variation 95% confidence intervals will be presented for selective PD, PK, and ADA endpoints. All results will be presented for all subjects and by treatment group using analysis population as appropriate.

All statistical analyses will be performed using Statistical Analysis Software (SAS) version 9.4 (or higher), R version 4.0.2 (or higher) and Phoenix WinNonlin version 8.3.1 (or higher).

